1.6.3 Warnings and Precautions

1.6.3.1 Tumor Lysis Syndrome (TLS)

Tumor lysis syndrome, including fatal events, has occurred in patients with previously treated CLL with high tumor burden when treated with venetoclax.

Venetoclax can cause rapid reduction in tumor, and thus poses a risk for TLS in the initial 5 weeks dose titration phase. Changes in electrolytes consistent with TLS that require prompt management can occur as early as 6 to 8 hours following the first dose of venetoclax and at each dose increase.

The risk of TLS is a continuum based on multiple factors, including comorbidities. Patients with high tumor burden (e.g., any lymph node with a diameter ≥5 cm or high ALC ≥25 x 109/l) are at greater risk of TLS when initiating venetoclax. Reduced renal function (CrCl <80 ml/min) further increases the risk. Patients should be assessed for risk and should receive appropriate prophylaxis for TLS, including hydration and anti hyperuricaemics. Blood chemistries should be monitored, and abnormalities managed promptly. Dosing should be interrupted if needed. More intensive measures (intravenous hydration, frequent monitoring, hospitalization) should be employed as overall risk increases. The instructions for "Prevention of tumor lysis syndrome" should be followed.

Concomitant use of this medicinal product with strong or moderate CYP3A inhibitors increases venetoclax exposure and may increase the risk for TLS at initiation and during the dose-titration phase. Also inhibitors of P-gp or BCRP may increase venetoclax exposure. In the initial Phase 1 dose-finding studies, which had a shorter (2 to 3 week) titration phase and higher starting dose, the incidence of TLS was 13% (10/77; 5 laboratory TLS; 5 clinical TLS), including 2 fatal events and 3 events of acute renal failure, 1 requiring dialysis.

The risk of TLS was reduced after revision of the dosing regimen and modification to prophylaxis and monitoring measures. In venetoclax clinical studies, patients with any measurable lymph node \geq 10 cm or those with both an ALC \geq 25 x 10 9 /l and any measurable lymph node \geq 5 cm were hospitalized to enable more intensive hydration and monitoring for the first day of dosing at 20 mg and 50 mg during the titration phase.

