In 168 patients with CLL starting with a daily dose of 20 mg and increasing over 5 weeks to a daily dose of 400 mg in studies M13-982 and M14-032, the rate of TLS was 2%. All events were laboratory TLS (laboratory abnormalities that met \geq 2 of the following criteria within 24 hours of each other: potassium >6 mmol/l, uric acid >476 μ mol/l, calcium <1.75 mmol/l, or phosphorus >1.5 mmol/l; or were reported as TLS events) and occurred in patients who had a lymph node(s) \geq 5 cm or ALC \geq 25 x 10 9 /l. No TLS with clinical consequences such as acute renal failure, cardiac arrhythmias or sudden death and/or seizures was observed in these patients. All patients had CrCl \geq 50 ml/min.

In the open-label, randomized phase 3 study (MURANO), the incidence of TLS was 3% (6/194) in patients treated with venetoclax + rituximab. After 77/389 patients were enrolled in the study, the protocol was amended to incorporate the current TLS prophylaxis and monitoring measures described in Posology (see section 4.2). All events of TLS occurred during the venetoclax dosetitration phase and resolved within two days. All six patients completed the dose titration and reached the recommended daily dose of 400 mg of venetoclax. No clinical TLS was observed in patients who followed the current 5-week dose-titration schedule and TLS prophylaxis and monitoring measures (see section 4.2). The rates of grade ≥3 laboratory abnormalities relevant to TLS were hyperkalemia 1%, hyperphosphatemia 1%, and hyperuricemia 1%.

For details regarding risk factors, prophylactic measures and handling of TLS see appendix 6.

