3.6 SELECTION OF STUDY POPULATION

3.6.1 Inclusion Criteria

Eligible subjects will be considered for inclusion in this study if they meet all the following criteria:

- 1. CLL diagnosed according to IWCLL criteria within one year prior to randomization
- 2. High risk of infection and/or progressive treatment within 2 years according to CLL-TIM
- 3. IWCLL treatment indication not fulfilled
- 4. Life expectancy > 2 years
- 5. Age at least 18 years
- 6. Ability and willingness to provide written informed consent and adhere to study procedures and treatment
- 7. Adequate bone marrow function as indicated by platelets above 100 x 10E9, hemoglobin above 10 g/dL and neutrophils above 1 x 10E9
- 8. Creatinine clearance above 30 mL/min directly measured with 24hr urine collection or calculated according to the modified formula of Cockcroft and Gault
- 9. Adequate liver function as indicated by a total bilirubin≤ 2 x, AST or ALT ≤ 2.5 x the institutional ULN value, unless directly attributable to the patient's CLL or to Gilbert's Syndrome.
- 10. Negative serological testing for hepatitis B (HBsAg negative and anti-HBc negative; patients positive for anti-HBc may be included if PCR for HBV DNA is negative and HBV-DNA PCR is performed every month until 12 months after last treatment cycle), negative testing for hepatitis C RNA within 6 weeks prior to registration.
- 11. Eastern Cooperative Oncology Group Performance Status (ECOG) performance status 0-2.
- 12. Woman of childbearing potential (WOCBP) who are sexually active must use highly effective methods of contraception during treatment and for 30 days after the last dose of investigational drugs.
- 13. Willing and able to participate in all required evaluations and procedures in this study protocol including swallowing capsules without difficulty.
- 14. Ability to understand the purpose and risks of the study and provide signed and dated informed consent and authorization to use protected health information.

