3.8 STUDY TREATMENT SCHEDULE

Acalabrutinib will be administered orally 100 mg twice daily, every day from cycle 1 day 1 for 3 cycles of 28 days each.

Venetoclax, ramp up during the first five weeks starting cycle 1 day 1, 7 days treatment on each dose level (20-50-100-200-400 mg), thereafter 400 mg once daily for a total of 3 cycles of 28 days counted from cycle 1 day 1.

Please see section 3.9 for management of dosing delays and modifications.

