3.10.2 Dosing Delays and Modification for Venetoclax

Dose modification for TLS and other toxicities.

Dose at interruption (mg)	Restart dose (mg ^a)
400	300
300	200
200	100
100	50
50	20
20	10
aThe modified dose should	

before increasing the dose.

For patients who have had a dosing interruption lasting more than 1 week during the first 5 weeks of dose titration or more than 2 weeks after completing the dose-titration phase, TLS risk should be reassessed to determine if restarting at a reduced dose is necessary (e.g., all or some levels of the dose titration).

Venetoclax Recommended Dose Modifications for Toxicities

Event	Occurrence	Action				
Tumor Lysis Syndrome						
Blood chemistry changes or symptoms suggestive of TLS (Cairo-Bishop grading in Appendix 6)	Any	Withhold the next day's dose. If resolved within 24-48 hours of last dose, resume at the same dose.				
		For any blood chemistry changes requiring more than 48 hours to resolve, resume at one dose level reduction				
		For any events of clinical TLS, resume at one dose level reduction following resolution				
Non-Hematologic Toxicit	ties					
Grade 3 or 4 non- hematologic toxicities	1 st occurrence	Interrupt venetoclax Once the toxicity has resolved to Grade 1 or baseline level, venetoclax therapy may be				

Event	Occurrence	Action				
		resumed at the same dose. No dose modification is required.				
	2 nd and subsequent occurrences	Interrupt venetoclax. Restart at one dose level reduction when resuming treatment with venetoclax after resolution. A larger dose reduction may occur the discretion of the investigator.				
Hematologic Toxicities						
Grade 3 or 4 neutropenia with infection or fever; or Grade 4 hematologic toxicities (except lymphopenia)	1 st occurrence	Interrupt venetoclax. To reduce the infection risks associated with neutropenia, granulocyte-colony stimulating factor (G-CSF) may be administered with venetoclax if clinically indicated. Once the toxicity has resolved to Grade 1 or baseline level, venetoclax therapy may be resumed at the same dose.				
	2 nd and subsequent occurrence	Interrupt venetoclax. Consider using G-CSF as clinically indicated. Restart at one dose level reduction when resuming treatment with venetoclax after resolution. Additional dose reductions may occu at the discretion of the physician. Re-escalation on the discretion of the treating physician				

Patients who require dose reductions to less than 100 mg for more than 4 weeks should stop treatment.

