Laboratory tumor lysis syndrome (LTLS) is defined as either a 25% change or level above or below normal, as defined above, **for any two or more serum values** of uric acid, potassium, phosphate, and calcium within 3 days before or 7 days after the initiation of chemotherapy. This assessment assumes that a patient has or will receive adequate hydration (± alkalinization) and a hypouricaemic agent(s) (Cairo, 2004).

Clinical Tumor Lysis Syndrome (CTLS):

Clinical tumor lysis syndrome (CTLS) assumes the laboratory evidence of metabolic changes and significant clinical toxicity that requires clinical intervention.

The presence of LTLS and one or more of the following criteria:
Creatinine: ≥ 1.5 ULN *
Cardiac arrhythmia / sudden death*
Seizure*

(*Not directly or probably attributable to a therapeutic agent (e.g. rise in creatinine after amphotericin administration)). (Cairo, 2004)

Cairo-Bishop Tumor Lysis Syndrome Grading

ino bishop rumor Lysis dynarome Ordanig								
#	Grade 0	Grade 1	Grade 2	Grade 3	Grade 4	Grade 5		
LTLS	-*	+	+	+	+	+		
Creatinine#	≤ 1.5 x ULN	1.5 x ULN	> 1.5-3.0 x ULN	> 3.0-6.0 x ULN	> 6.0 x ULN	Death\$		
Cardiac arrythmia#	None	Intervention not indicated	Nonurgent medical intervention indicated	Symptomatic and incompletely controlled medically or controlled with	Life-threatening (e.g., arrhythmia associated with CHF.	Death ^{\$}		
				device (e.g., defibrillator)	hypotension, syncope, shock			
Seizure#	None	-	One brief, generalized seizure; seizures(s) well controlled by anticonsulvants; or infrequent focal motor seizures not interfering with ADL	Seizures in which consciousness is altered; poorly controlled seizure disorder, with breakthrough generalized seizure despite medical intervention	Seizures of any kind which are prolonged, repetitive, or difficult to control (e.g., status epilepticus, intractable epilepsy)	Death ^{\$}		

CTLS requires one or more clinical manifestations along with criteria for LTLS Maximal CTLS manifestation (renal, cardiac, neuro) defines the grade

- * No LTLS
- * Not directly or probably related to a therapeutic agent
- \$ Attributive probably or definitely to CTLS

Further actions need to be taken in case of:

- potassium increase by ≥0.5mmol/l from baseline and/or any potassium value >5.0 mmol/l
- phosphorus increase of >0.5 mg/dl 0.16 mmol/l and >4.5 mg/dl 1,45 mmol/l
- any other significant laboratory change, especially electrolyte imbalances

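### The laboratory TLS window in Appendix 6 is tied to chemotherapy that this trial does not give; read as first study dose, it closes at about day 8, before three of the five venetoclax dose steps

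*Protocol*

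**What the plan says.** **The definition.** Appendix 6, under the scoring of tumor lysis syndrome, tells sites to diagnose laboratory and clinical TLS by the Cairo-Bishop criteria. Laboratory TLS needs two or more abnormal values among uric acid, potassium, phosphate and calcium "within 3 days before or 7 days after the initiation of chemotherapy". Clinical TLS is laboratory TLS plus a creatinine, cardiac or seizure criterion. In the grading table laboratory TLS is absent at grade 0 and present at grades 1 to 5.

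**The treatment.** Section 3.11.2 prohibits cytotoxic chemotherapy. Section 3.8 starts acalabrutinib and venetoclax together on cycle 1 day 1 and ramps venetoclax with "7 days treatment on each dose level (20-50-100-200-400 mg".

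**The risk period.** Section 1.6.3.1 says that electrolyte changes consistent with TLS can appear within hours "following the first dose of venetoclax and at each dose increase".

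**Rules that use the label.** The TLS row of the venetoclax dose table in section 3.10.2 is headed "Blood chemistry changes or symptoms suggestive of TLS (Cairo-Bishop grading in Appendix 6". Its first instruction is to withhold the next day's dose, and then "If resolved within 24-48 hours of last dose, resume at the same dose". Slower chemistry, or any clinical TLS, means restarting one dose level lower. Section 4.1.3 makes clinical TLS an SAE in every case.

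**The concern.** The window suits a treatment with a single start. Here its anchor never occurs, and the natural substitute, first study dose, leaves most of the ramp-up uncovered. The protocol orders chemistry at every dose step but defines TLS so that most of the later results cannot count. No sentence moves the window to venetoclax or to each step.

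What is at stake is classification. A late event handled strictly by the text could go without a TLS diagnosis and without a Cairo-Bishop grade. Two mandatory consequences depend on that label: SAE reporting of clinical TLS in every case (section 4.1.3), and the one-level reduction after clinical TLS when the chemistry settles within 48 hours (section 3.10.2). Sites that read the window differently would also classify the same event differently.

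**Working it through.** **Inputs**
- Ramp: five levels of 7 days from cycle 1 day 1 (section 3.8).
- Window: ends 7 days after the start of treatment (Appendix 6). The start is taken as day 1. This is an assumption, because the literal anchor does not exist.
- Post-dose samples, low and medium risk: 6–8 h and 24 h at 20 and 50 mg, then 24 h at the other steps (Appendix 6, initial dosing and monitoring).
- Post-dose samples, high risk: either 6–8 h and 24 h at all five levels (same place), or 4, 8, 12 and 24 h at 20 and 50 mg followed by 6–8 h and 24 h (Appendix 6, laboratory assessments).

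**Reproducing the ramp.** Step start = 1 + 7i for i = 0 to 4, so 20, 50, 100, 200 and 400 mg start on days 1, 8, 15, 22 and 29. The ramp ends on day 29 + 6 = 35, which is the stated five weeks. It also agrees with the table in section 3.7.5, where 400 mg begins on cycle 2 day 1, that is day 28 + 1 = 29.

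**Window against steps.** Window end = day 1 + 7 = day 8.
- 20 mg (day 1): inside.
- 50 mg (day 8): on the edge. Same-day samples are inside and the 24 h sample (day 9) is outside.
- 100, 200 and 400 mg (days 15, 22, 29): wholly outside, so 3 of 5 steps.
- Ramp days outside: 35 − 8 = 27.

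**Post-dose samples outside, by calendar day**
- Low and medium risk: total 2+2+1+1+1 = 7; outside on days 9, 16, 23 and 30 = 4; 4/7 = 57%.
- High risk, first schedule: total 5 × 2 = 10; outside 1+2+2+2 = 7; 7/10 = 70%.
- High risk, second schedule: total 4+4+2+2+2 = 14; outside 1+2+2+2 = 7; 7/14 = 50%.

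**If 7 days means 168 hours.** The 50 mg dose falls at hour 168, so all its post-dose samples are also outside: 5/7 = 71%, 8/10 = 80% and 10/14 = 71%.

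**If a site restarts the window at each step.** The share is 0.

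**After re-anchoring.** Windows from 3 days before to 7 days after days 1, 8, 15, 22 and 29 overlap and cover 35 of 35 ramp days and every scheduled post-dose sample.

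These are shares of samples, not of events. The number of events affected cannot be computed, because the protocol gives no TLS counts by dose step. The earlier-study rates in section 1.6.3.1 also rest on a different rule: absolute limits met within 24 hours of each other, or a reported TLS event. Appendix 6 additionally accepts a 25% change from baseline.

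**The case against.** The strongest reply is that the protocol, read as a whole, looks for TLS at every step. Appendix 6 tells sites to monitor high-risk patients for TLS at the first dose of each level, section 3.10.2 applies its TLS row to any occurrence, and the word chemotherapy is simply carried over from the cited source definition. A sensible site may well apply the window per step. This stands as a likely practice, but the per-level wording governs when samples are drawn, not what counts as TLS.

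The consequences are also narrow, and this part of the reply largely stands. Four stronger readings are tempting, and the protocol does not support them:
- *Late events would be ungraded.* Sections 3.4.2 and 4.1.4 and Appendix 8 grade adverse events by CTCAE version 5, with a fallback scale in section 4.1.4 and no time window. Only the Cairo-Bishop grade would be missing.
- *Late events would go unmanaged.* Dose holds apply at any dose, and the further actions in Appendix 6 are triggered by laboratory changes with no window. The extra measures reserved for an established TLS diagnosis are only to be considered, per institutional practice, so nothing mandatory is lost there.
- *Late events would go unreported.* Tumor lysis events are AESIs without a time limit (sections 4.1.3 and 6.1.5), and many late clinical events would be SAEs through hospitalization or another criterion.
- *Many events would be missed.* Section 1.6.3.1 points to rarity. For the randomized study of venetoclax plus rituximab it says "No clinical TLS was observed in patients who followed the current 5-week dose-titration schedule". For 168 monotherapy patients it says "No TLS with clinical consequences such as acute renal failure, cardiac arrhythmias or sudden death and/or seizures was observed in these patients". The reassurance is not complete: those 168 all had creatinine clearance of at least 50 ml/min, while this trial's criterion is "Creatinine clearance above 30 mL/min directly measured with 24hr urine collection" or the calculated equivalent. Appendix 6 does handle patients at 30–50 ml/min as high risk.

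**Conclusion.** The point holds as a minor error in a definition. As written, the window has no valid anchor. Read as first study dose, it excludes three of the five dose steps, the 24-hour sample of a fourth, and 50% to 70% of the scheduled post-dose TLS samples by calendar day (71% to 80% if counted as 168 hours).

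The exposure is limited to the TLS diagnosis and Cairo-Bishop grade of late events, the automatic SAE rule for clinical TLS, the one-level reduction after a clinical event whose chemistry resolves within 48 hours, and consistent classification across sites. The conclusion assumes that sites follow the text literally; where they apply the window per step, nothing is lost. The primary endpoint, grade 3 or higher infection-free survival at 24 weeks, does not use TLS and is unaffected, as are the margin and sample size.

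**What to change.** In the laboratory TLS definition of Appendix 6, replace the time phrase with: *from 3 days before to 7 days after the first venetoclax dose, any venetoclax dose increase or any restart*. Restart belongs there because section 3.10.2 asks for TLS risk to be reassessed after longer interruptions. Add one sentence stating that this definition applies to Cairo-Bishop grading, to the clinical TLS rule in section 4.1.3 and to the TLS rows of section 3.10.2.

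The cost is a short text change at the next amendment. No new samples are needed, because Appendix 6 already requires chemistry at every ramp-up step. The downside is that a few more events may be labelled TLS.

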Appendix 7. Charlson Comorbidity Index

Clinical Condition	Weight
Myocardial infarction	1
Congestive heart failure	1
Peripheral vascular disease	1
Dementia	1
Cerebrovascular disease	1
Chronic pulmonary disease	1
Connective tissue disease	1
Ulcer disease	1
Mild liver disease	1
Slight diabetes without complications	1
Hemiplegia	2
Moderate or severe renal disease	2
Diabetes with end organ damage	2
Tumors	2
Leukemia	2
Lymphoma	2
Moderate or severe liver disease	3
Metastatis solid tumor	6
Acquired immunodeficiency syndrome	6

M. Charlson, T.P. Szatrowski, J. Peterson, et al. Validation of a combined comorbidity index J Clin Epidemiol, 47 (1994), pp. 1245–1251

Appendix 8. Response and Outcome assessment

According to IWCLL guidelines 2018, Hallek et al., Blood, 2018

Table 4. Response definition after treatment of CLL patients

Group	Parameter	CR	PR	PD	SD
А	Lymph nodes	None ≥1.5 cm	Decrease ≥50% (from baseline)*	Increase ≥50% from baseline or from response	Change of -49% to +49%
	Liver and/or spleen size <13 cm; Decrease ≥50% (from baseline) Increase ≥50% from baseline or from response			Change of -49% to +49%	
	Constitutional None symptoms		Any	Any	Any
	Circulating lymphocyte count	Normal	Decrease ≥50% from baseline	Increase ≥50% over baseline	Change of -49% to +49%
В	Platelet count	≥100 × 10°/L	≥100 × 10°/L or increase ≥50% over baseline	Decrease of ≥50% from baseline secondary to CLL	Change of -49 to +49%
	Hemoglobin ≥11.0 g/dL (untransfused and without erythropoietin) ≥11 g/dL or increase ≥50% over baseline baseline secondary to CLL		Increase <11.0 g/dL or <50% over baseline, or decrease <2 g/dL		
	Marrow	Normocellular, no CLL cells, no B-lymphoid nodules	Presence of CLL cells, or of B-lymphoid nodules, or not done	Increase of CLL cells by ≥50% on successive biopsies	No change in marrow infiltrate

For a detailed description of the response parameters, see section 5.

Complete remission

CR requires all of the following criteria (see Table 4 above).

- 5.1.1. Peripheral blood lymphocytes (evaluated by blood and differential count),≤4.3 10⁹/L.
- 5.1.2. Absence of significant lymphadenopathy by physical examination. In clinical trials, a CT scan of the neck, abdomen, pelvis, and thorax is desirable if previously abnormal. Lymph nodes should be ≤1.5 cm in longest diameter. Once this is determined, further imaging should not be required until disease progression is apparent by clinical examination or on blood testing.
- 5.1.3. No splenomegaly or hepatomegaly by physical examination. In clinical trials, a CT scan of the abdomen should be performed at response assessment and should show no evidence for lymphadenopathy and splenomegaly. We propose to use a recent consensus response cutoff for splenomegaly of 13 cm in craniocaudal length. However, the persistence of splenomegaly may not correlate with outcome. The quantitative determination of hepatomegaly seems more difficult; changes such as focal or disseminated hepatic nodules support liver involvement.
- 5.1.4. Absence of disease-related constitutional symptoms.
- 5.1.5. Blood counts need to show the following values:
- 5.1.5.1. Neutrophils ≥1.5 10⁹/L.

^{*}Sum of the products of 6 or fewer lymph nodes (as evaluated by CT scans and physical examination in clinical trials or by physical examination in general practice).

[†]Spleen size is considered normal if <13 cm. There is not firmly established international consensus of the size of a normal liver; therefore, liver size should be evaluated by imaging and manual palpation in clinical trials and be recorded according to the definition used in a study protocol.

CR, complete remission (all of the criteria have to be met); PD, progressive disease (at least 1 of the criteria of group A or group B has to be met); PR, partial remission (for a PR, at least 2 of the parameters of group A and 1 parameter of group B need to improve if previously abnormal; if only 1 parameter of both groups A and B is abnormal before therapy, only 1 needs to improve); SD, stable disease (all of the criteria have to be met; constitutional symptoms alone do not define PD).

- 5.1.5.2. Platelets ≥100 10⁹/L.
- 5.1.5.3. Hemoglobin ≥11.0 g/dL (without red blood cell transfusions).
- 5.1.6. MRD assessment.

In clinical trials aimed at maximizing the depth of remission, the presence of MRD after therapy should be assessed (see section 5.9). The sensitivity of the method used to evaluate for MRD should be reported, as should the tissue studied (blood or marrow). The proportion of patients achieving undetectable MRD should be reported with the total number of patients treated with the specific therapy as the denominator (not as a proportion of responders or those in CR). 5.1.7. For patients in clinical trials, a bone marrow aspirate and biopsy should be performed if clinical and laboratory results listed in sections 5.1.1 to 5.1.5 demonstrate that a CR may have been achieved. To define a CR, the cytological or pathological evaluation of the bone marrow smear or biopsy must be at least normocellular for age, without evidence for typical CLL lymphocytes by morphological criteria. This evaluation is not based on a flow cytometry-based MRD assessment. In a clinical trial, the time point of marrow biopsy should be defined by the protocol. For example, in patients receiving chemo(immuno)therapy, the time point of marrow biopsy is typically 2 months posttherapy. When performing marrow biopsies in clinical trials, lymphoid nodules can be found that may reflect residual disease. These nodules may be recorded as "nodular partial remission." Immunohistochemistry may be performed to define whether the nodules comprise primarily T cells, B cells other than CLL cells, or CLL cells. If nodules are not composed of CLL cells, a CR can be documented provided all other criteria are met. If the marrow is hypocellular, a repeat determination should be performed 4 weeks or later, when peripheral blood counts have recovered; however, this interval should not exceed 6 months after the last treatment. In cases in which a marrow biopsy was obtained at baseline, a comparison of pre-vs posttherapy biopsies should be performed. In general practice, the use of a marrow biopsy for evaluating a CR is at the discretion of the physician. In clinical trials aimed at maximizing the response rate, the quality of the response should be assessed in the marrow for MRD by highly sensitive molecular-based assays or immunophenotyping (see section 5.9). 5.1.8. Some patients fulfill all the criteria for a CR (including the marrow examinations described in section 5.1.7), but have a persistent anemia, thrombocytopenia, or neutropenia apparently unrelated to CLL, but related to drug toxicity. These patients should be considered as a different category of remission, CR with incomplete marrow recovery (CRi). For the definition of this category, the marrow evaluation (see section 5.1.7) should be performed with scrutiny and not show any clonal disease infiltrate. In clinical trials, patients having CR with incomplete marrow recovery should be monitored prospectively to determine whether their outcome differs from that of patients with detectable residual

Partial remission

disease or with noncytopenic CR.

To define a partial remission, at least 2 parameters of group A and 1 parameter of group B need to improve, if previously abnormal (Table 4; sections 5.2.1 to 5.2.5). If only 1 parameter of both groups A and B was abnormal before therapy, only 1 needs to improve. Constitutional symptoms persisting for ≥1 month should be recorded.

- 5.2.1. A decrease in the number of blood lymphocytes to 50% or less from the value before therapy.
- 5.2.2. Reduction in lymphadenopathy compared with baseline (by cross-sectional imaging scans in clinical trials or by palpation in general practice) as defined by:
- 5.2.2.1. A decrease in lymph node size by 50% or more in n the sum of the products of the same enlarged lymph nodes selected at baseline as assessed by imaging (an established number in clinical trials of lymph nodes has been up to 6). n and the sum of longest diameters of the same enlarged lymph nodes selected at baseline as assessed by physical examination (an established number in clinical trials of lymph nodes has been a maximum of 6).

- 5.2.2.2. No increase in any lymph node and no new enlarged lymph node (diameter ≥1.5 cm). For small lymph nodes (longest diameter ≤1.5 cm), an increase ≤25% is not considered significant. 5.2.3. A regression ≥50% of the extent of enlargement of the spleen below the costal margin defined by palpation, or normalization in size. When assessed by CT, scan spleen size must have regressed by ≥50% in length beyond normal.96 A persistence of splenomegaly posttherapy may have limited influence on outcome in CLL.
- 5.2.4. A regression of ≥50% of the extent of enlargement of the liver below the costalmargin defined by palpation, or normalization in size. Given the impact of numerous medical conditions, liver size by physical examination or CT scan is not a reliable measure of hepatic involvement by CLL and should only be counted if hepatomegaly is clearly attributable to lymphoid involvement.
- 5.2.5. The blood count should show 1 of the following results:
- 5.2.5.1. Platelet counts ≥100 10⁹/L or 50% improvement over baseline.
- 5.2.5.2. Hb ≥11.0 g/dL or 50% improvement over baseline without red blood cell transfusions or erythropoietin support.

Infectious event

Grading of all adverse events are according to Common Terminology Criteria for Adverse Events (CTCAE), Version 5. For the primary outcome of the optional phase 3 part of the study, any infectious events leading to an SAE will be considered at least grade 3, thus counting as an event for the primary outcome.

